### **Residual Tumor Assessment**

A single 2-mm or 3-mm punch biopsy or up to three 2-mm or three 3-mm sampling punch biopsies will be performed on the residual tumor.

- Biopsy must be performed in area not previously biopsied.
- Biopsy of residual tumor should be performed at least 1 mm from the peripheral margin of visible or palpable lesion
- Tumor biopsies performed at Week 24 visit will comprise no more than 10% of visible lesion surface area.

### **Area of Tumor Clearance Assessment**

Up to three 2-mm or three 3-mm punch biopsies will be performed on the area of tumor clearance at Week 24 when possible.

[figure not shown]

Figure 4. Site of biopsies for tumors that display partial response or stable disease at Week 24 visit.

#### 6.1.5 Early Termination

If a subject discontinues from the study early (due to patient decision to discontinue or disease progression), the study procedures will be completed as described for Week 24.

#### 6.1.6 Surgery visit

Subjects that are found to have histologic evidence of disease on biopsies performed at Week 24 visit will undergo surgical excision. This visit should be scheduled to occur with 4 weeks of last dose of study drug and will be performed as standard of care treatment.

For lesions that display clinical partial response or stable disease and that show histologic evidence of disease on sampling biopsy at Week 24 visit, residual visible or palpable tumor of target lesion will be removed using the standard Slow Mohs micrographic surgery, margin-controlled excision with rush permanent sections. Two types of specimens will be surgically removed at the time of surgical excision. First, the area of known BCC will be excised and will include the pre-biopsy area. This specimen will be labeled the tumor “debulking” specimen.

Second, marginal tissue will be excised in an attempt to completely remove the tumor until clear surgical margins are obtained, providing the patient the known standard of care. This tissue will be labeled “tumor margins” specimen. Peripheral and deep margins will be examined and recorded if positive or negative. If either peripheral or deep margins is positive, additional surgical excisions will be done in the Mohs tissue orientation fashion until no tumor cells are observed and surgical margins are deemed negative, as is standard of care. In the event that only superficial BCC (sBCC) remains at the surgical margin, it will be at the discretion of the managing physician if further surgery, an alternative treatment modality, or observation will occur.

For lesions that were deemed by investigator to exhibit complete clinical response at week 24 visit, but were found to have residual disease on the sampling biopsy at week 24 visit, the debulking specimen will include area of known BCC as seen on histology.

#### 6.1.7 **Study Exit Visit (Post-Surgery Visit)**

This study visit should be scheduled to occur within 4 weeks of surgical excision or Mohs surgery, performed as standard of care treatment.

The following procedures will be performed:

- Assessment of any changes (deletions, additions, or dose modifications) to medications (noting exclusions, restrictions, and prohibited medications)
- Complete physical examination including general appearance, skin exam, and visual inspection of surgical site of target lesion(s).
- Vital signs (BP; heart or pulse rate; and oral, tympanic, or temporal temperature).
- Weight and high measurements.
- Urine pregnancy test ( $\alpha$ -hCG) only for women who are of childbearing potential.
- Surgical site photography
- Adverse Event (AE) Monitoring.

#### 6.1.8 **Observation period**

All subjects will be followed for the observation period of 1 year after discontinuation of study medication.

During the observation period the subjects will followed every 3 months for 1 year after last dose.

The following study procedures during observation period:

- Assessment of any changes (deletions, additions, or dose modifications) to medications.
- Complete physical examination including general appearance, skin exam, and visual inspection of target lesion(s) area.
- Vital signs (BP; heart or pulse rate; and oral, tympanic, or temporal temperature).
- Weight and height measurements.
- Urine pregnancy test ( $\alpha$ -hCG) only for women who are of childbearing potential for visits within 7 months of last dose of study drug.
- Photography and measurement of target lesion area
- Adverse Event (AE) Monitoring.
- Reminder to use effective measures to avoid pregnancy (for women who are of child bearing potential for visits within 7 months of last dose of study drug).
- PRO questionnaires will be performed by the subject (SKINDEX-16 and Functional Assessment of Cancer Therapy – General (FACT-G) at first visit during Observation period (3 months after discontinuing treatment).

If a subject is noted to have a recurrence of target lesion or new lesions suspicious for BCCs on any part of the body, biopsy will be performed to confirm diagnosis. If pathology is consistent with basal cell carcinoma, the subject will exit the Observation period and all treatment options

will be discussed with the subject. If Mohs micrographic surgery is determined to be the best therapeutic option, surgical excision and study procedures will be performed as described in Section 6.1.6.

Subjects who underwent surgical excision of the target lesion may elect to be followed by phone contact every 3 months to provide information on the status of the surgical site and occurrence of any adverse events.

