##### 4.1 INCLUSION CRITERIA

Subjects must meet all of the following inclusion criteria to be eligible for enrollment into the study:

1. Evidence of a personally signed and data informed consent document indicating that the subject (or legally acceptable representative) has been informed of all pertinent aspects of the trial.
2. Subjects who are willing to comply with scheduled visits, treatment plan, laboratory tests, and other study procedures.
3. Be 18 years of age or older at the time of informed consent.
4. Has one or more clinically suspicious lesions for BCC at Pre-Study screening Visit that is/has:
  - a. a diameter  $\geq$  6 mm if located on the “mask areas” of face (central face, eyelids, eyebrows, periorbital, nose lips [cutaneous and vermillion], chin, mandible, preauricular and postauricular skin/sulci, temple, ear), genitalia, hands, or feet (See Appendix 2 for Figure of “mask areas” of face)
  - b. a diameter  $\geq$  10 mm if located on cheeks, forehead, scalp, or neck
  - c. a diameter  $\geq$  20 mm if located on trunk and extremities

or has a lesion suspicious for locally advanced BCC defined as a lesion that:

- a. is  $\geq$  10 mm,
  - b. has recurred following surgery or surgical resection would result in substantial deformity, and
  - c. has been deemed not appropriate for radiation.
5. Have a histologically-confirmed BCC prior to first dose of study drug at Treatment Initiation Visit (Baseline/Day 1).
  6. Have an Eastern Cooperative Oncology Group (ECOG) performance status of 2 or less at Baseline/Day 1 visit. (See Appendix 3, ECOG Performance Status)
  7. Males and females must agree that they have no desire or plan to conceive children in the future
  8. Female of reproductive potential must use 2 effective methods to avoid pregnancy during therapy and for 9 months after completing therapy. Effective methods must be used for 1 month before initiating therapy.
  9. Male patients must use effective measures to avoid pregnancy in their partner at all times, even after vasectomy, during treatment and for 3 months after the last dose.
  10. Agreement not to donate blood or blood products during the study and for 9 months after the last dose.
  11. Subjects with Basal Cell Nevus Syndrome are eligible for enrollment.

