- Females are reminded that they must use 2 effective methods to avoid pregnancy for 1 month prior to start of study medication, during therapy, and for 9 months after completing therapy.
- For women who do not want to conceive in the future but are still women of childbearing potential:
  - Two negative pregnancy tests with a sensitivity of at least 25 mIU/mL at least 19 days apart
  - For patients with regular menstrual cycles, the second pregnancy test should be done during the first 5 days of the menstrual period immediately preceding the beginning of therapy and after the patient has used 2 effective measures to avoid pregnancy for 1 month.
  - For patients with amenorrhea, irregular cycles, or using a contraceptive method that precludes withdrawal bleeding, the second pregnancy test must be done immediately preceding the beginning of therapy and after the patient has used 2 effective measures to avoid pregnancy for 1 month.
- Laboratory evaluation at baseline to evaluate abnormalities in hematocrit/platelet counts, renal or hepatic function and electrolytes.

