## **6.5 SUBJECT COMMITMENT TO STUDY**

The duration of each subject's participation in the study will be approximately 28 weeks. Subjects will be expected to visit the clinic for 10 scheduled study visits. Up to 12 (three sampling biopsies on 4 possible target lesions) will be performed at the pre-study screening visit, 12 punch biopsies at Week 12 visit and a complete Mohs excision may be performed at the target tumor site at the Mohs procedure visit within 4 weeks after the end-of-treatment visit. Subjects are expected to adhere to daily administration of medication during 24 weeks of treatment and take appropriate measures to avoid pregnancy and avoid donation of blood up to 9 months after last dose.

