#### 6.8 **PREGNANCY**

Vismodegib is teratogenic. As clinical studies of vismodegib have not been conducted in pregnant humans, subjects who become pregnant during the study must inform the investigator immediately of their pregnancy, and agree to provide follow-up information regarding the outcome of the pregnancy. In addition, there is the unknown potential irreversible affect on fertility with data showed in earlier studies of amenorrhea. Subjects (male and female) who desire to conceive in the future are excluded from the study.

Females of reproductive potential must use effective measures to avoid pregnancy during therapy and for 1 month prior to the start of the study medication, and for 9 months after completing therapy. Male patients must use effective measures to avoid pregnancy in their partner, even after vasectomy, during sexual intercourse with females during treatment and for 3 months after the last dose to avoid exposing a pregnant partner and the unborn fetus to vismodegib. Vismodegib is contraindicated in nursing mothers during treatment and for 9 months after the last dose. In addition, subjects will be instructed not to donate blood or blood products while on treatment and for 9 months after the last dose of vismodegib.

The anticipated pregnancy prevention program includes the following measures for women of childbearing potential:

- a) two negative pregnancy tests with a sensitivity of at least 25 mIU/mL at least 19 days apart prior to starting study medication. For patients with regular menstrual cycles, the second pregnancy test should be done during the first 5 days of the menstrual period immediately preceding the beginning of therapy and after the patient has used 2 forms of contraception for 1 month. For patients with amenorrhea, irregular cycles, or using a contraceptive method that precludes withdrawal bleeding, the second pregnancy test must be done immediately preceding the beginning of therapy and after the patient has used 2 forms of contraception for 1 month.
- b) Urine pregnancy test at each visit.
- c) Female patients must use 2 effective methods to avoid pregnancy for 1 month prior to start of study medication, during therapy, and for 9 months after completing therapy.

Male patients must use effective measures to avoid pregnancy in their partner at all times, even after vasectomy, for 3 months after the last dose (condom with spermicide is the effective method of contraception per approved labeling for vismodegib).

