
- a) Study medication will NOT be dispensed at each visit until the results of pregnancy have been reviewed by the study investigator.
- b) Reminder to use effective measures to avoid pregnancy will be performed throughout the study treatment for both men and women

Female patients do not have to follow the aforementioned measures to avoid pregnancy IF they agree to abide to the following conditions:

- have stopped having their period for 12 months in a row (menopause) and their doctor says they are in menopause or clinically fit the criteria for menopause
- had both of their ovaries or uterus taken out by surgery
- their ovaries do not work and they cannot get pregnant (confirmed by their doctor)

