#### 7.3.2.5 **Pregnancy**

If a female subject becomes pregnant while receiving investigational therapy or within 9 months after the last dose of VISMODEGIB, a report should be completed and expeditiously submitted to the Genentech, Inc. Follow-up to obtain the outcome of the pregnancy should also occur. Abortion, whether accidental, therapeutic, or spontaneous, should always be classified as serious, and expeditiously reported as an SAE. Similarly, any congenital anomaly/birth defect in a child born to a female subject exposed to the VISMODEGIB should be reported as an SAE.

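### Section 6.1.8 stops pregnancy tests and reminders at 7 months although women must avoid pregnancy for 9, which leaves out Observation Visit 3

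*Combined protocol and SAP*

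**What the plan says.** Section 6.1.8 sets the pregnancy safeguards after treatment in two bullets. The urine test is done "only for women who are of childbearing potential for visits within 7 months of last dose of study drug". The reminder bullet carries the same 7-month limit for the same women. In the text reviewed, 7 months appears only in these two bullets, and no reason is given for it.

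Elsewhere the period for women is 9 months. Under inclusion criterion 8 (Section 4.1) a woman of reproductive potential "must use 2 effective methods to avoid pregnancy during therapy and for 9 months after completing therapy". Sections 6.1.1 and 6.8 repeat this, and Section 6.5 expects subjects to "take appropriate measures to avoid pregnancy and avoid donation of blood up to 9 months after last dose". Section 7.3.2.5 makes a pregnancy reportable if it occurs on treatment or "within 9 months after the last dose of VISMODEGIB".

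Section 6.8 has two further lines that matter. Item b of the prevention program reads "Urine pregnancy test at each visit", with no end stated. The other line reads "Reminder to use effective measures to avoid pregnancy will be performed throughout the study treatment for both men and women".

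Appendix 6 has two tables with observation visits, one for complete response at Week 24 and one for complete response at Week 12. They do not mark the same observation visits for the test.

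**The concern.** Section 6.8 calls the drug teratogenic, and the protocol sets its own risk window at 9 months after last dose. Checks meant to support that window would be expected to run to its end. A site that follows Section 6.1.8 exactly would see a woman at Observation Visit 3, while she is still bound to avoid pregnancy, and neither test nor remind her. A site using the Week 12 table would test her at that visit but not remind her. Two sites could handle the same woman differently, and each could point to the protocol.

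What is at stake is subject safety and the completeness of pregnancy reporting within the 9-month window. Efficacy results are not involved.

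**Working it through.** The plan has no calculation to reproduce here. The inputs are the visit weeks and marks in Appendix 6, the 3-month spacing and 7-month limit in Section 6.1.8, and the 9-month duty in Sections 4.1 and 6.8. One month is taken as 30.44 days, and last dose as Week 24 or Week 12 according to the table.

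**Timing of the observation visits.** Weeks after last dose = visit week minus week of last dose; months = weeks × 7 / 30.44. The Week 24 table has visits at Weeks 36, 48, 60 and 72; the Week 12 table has them at Weeks 24, 36, 48 and 60. Both give the same intervals.

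| Observation visit | Weeks after last dose | Months (Appendix 6) | Months (3-month spacing) | Within 7 months | Within 9 months |
|---|---|---|---|---|---|
| 1 | 12 | 2.76 | 3 | yes | yes |
| 2 | 24 | 5.52 | 6 | yes | yes |
| 3 | 36 | 8.28 | 9 | **no** | **yes** |
| 4 | 48 | 11.04 | 12 | no | no |

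Visit 3 is the only visit that the two limits treat differently. It lies 8.28 − 7 = 1.28 months past the cut-off, or 9 − 7 = 2.0 months on 3-month spacing.

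**Marks in Appendix 6.** The Week 24 table has 12 columns, 8 of them before the observation period. The Week 12 table has 9 columns, 5 of them before it.

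| Row | Marks | Observation visits covered |
|---|---|---|
| Week 24 table, test | 10 of 12 | 1 and 2 |
| Week 24 table, reminder | 10 of 12 | 1 and 2 |
| Week 12 table, test | 9 of 9 | 1 to 4 |
| Week 12 table, reminder | 7 of 9 | 1 and 2 |

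Three of the four rows agree with Section 6.1.8. The Week 12 test row does not. Because the intervals after last dose are identical in the two tables, time since last dose cannot explain the difference.

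**What a test at Visit 3 gains.** Time from last scheduled test to the end of the 9 months:
- Last test at Visit 2: 9 − 5.52 = 3.48 months (3-month spacing: 9 − 6 = 3.0).
- Last test at Visit 3: 9 − 8.28 = 0.72 months (3-month spacing: 9 − 9 = 0).

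Of the 3.48 months, the step from Visit 2 to Visit 3 takes 84 / 30.44 = 2.76 months, or 2.76 / 3.48 = 79%. That part is ordinary visit spacing, and the fix adds no contact within it. The test still helps because it looks back over those 12 weeks.

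**What a reminder at Visit 3 gains.** It looks forward only. Nine months is 9 × 30.44 = 273.96 days and Visit 3 is at 36 × 7 = 252 days, which leaves 22 days. On 3-month spacing nothing is left.

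**The case against.** The strongest reply is that little depends on this visit. No drug is given in the observation period, so a positive test at Visit 3 could lead only to reporting and follow-up. Other safeguards exist: subjects must have no wish or plan to conceive (Section 4.1), they receive written instructions at Baseline (Section 6.1.2), they must report a pregnancy during the study at once (Section 6.8), and Visit 3 already includes an examination and adverse event monitoring. The reminder at Visit 3 has almost no preventive value. All of this stands and limits the size of the point. It does not explain the 7-month figure, and none of these safeguards is a scheduled test or reminder at Visit 3. The text of Appendix 8, the participant instructions, was not available, so whether it restates the 9 months could not be checked.

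Four stronger readings are tempting and are not supported:
- *The protocol lets women stop contraception at 7 months.* It does not. Section 6.1.8 limits the checks; the 9-month duty is unchanged wherever it appears.
- *Section 6.8 flatly contradicts Section 6.1.8 on testing.* Item b gives no end, but the same program ties dispensing to the test result and promises reminders during treatment. Its visits may be treatment visits only, and then Section 6.1.8 is the specific rule for observation. The firm conflict on testing is the Week 12 table.
- *The cut-off creates a 3.48-month gap.* Most of that is visit spacing, as shown above.
- *Women followed by phone after surgery have been left out.* Section 6.1.8 says all subjects are followed, and footnote 3 of Appendix 6 speaks of telephone visits. However, the sentence on phone contact names only the surgical site and adverse events. That is unclear rather than wrong.

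**Conclusion.** The point holds as a one-visit inconsistency in safety procedures. Section 6.1.8 ends tests and reminders at 7 months against a 9-month window that the protocol states repeatedly. Observation Visit 3 therefore loses both test and reminder under Section 6.1.8 and the Week 24 table, and loses the reminder under the Week 12 table. The Week 12 table separately conflicts with Section 6.1.8 by marking tests at all four observation visits. Section 6.8 item b leaves the end of testing open and does not settle which rule governs.

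The useful gain is the test; the reminder is worth adding mainly for consistency. The conclusion that Visit 3 is the affected visit holds under either spacing. The number of women of childbearing potential is not given, so the number affected cannot be stated. Endpoints, sample size and analyses are untouched.

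**What to change.** - **Section 6.1.8, both bullets:** replace the 7-month limit with *through Observation Visit 3 (9 months after last dose)*. Naming the visit matters because on 3-month spacing it falls exactly at 9 months.
- **Appendix 6, Week 24 table:** add the test and the reminder at Observation Visit 3.
- **Appendix 6, Week 12 table:** add the reminder at Observation Visit 3. The test mark at Visit 4 (11.04 months) goes beyond the window and is harmless; keep it as a deliberate extra, or remove it for consistency as a fourth table edit.
- **Section 6.8, item b:** refer to Section 6.1.8 for the observation period.
- **Optional clarification:** state that phone calls after surgery include the reminder for women of childbearing potential through 9 months.

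The cost is two wording changes, one cross-reference and three table marks, or four table edits if the Week 12 test mark is removed. Under the amended tables, each affected woman has one urine test and one reminder at a visit already scheduled (Week 24 pathway), or one reminder (Week 12 pathway, where the table already marks the test). No new visit is needed.

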## 6.2 METHODS OF ASSESSMENT

### 6.2.1 Measurement of Target Tumor

At the treatment initiation visit, the baseline size of the target tumor will be determined by measuring the 2 largest perpendicular diameters of the target tumor. Target tumor size will be measured at each visit

### 6.2.2 Clinical response evaluation of target lesion

Measurements of longest length and perpendicular diameter of target lesion(s) will be recorded at each interval visit and compared template map drawn treatment initiation visit.

**Complete response** will be defined as the disappearance of a palpable or visible tumor.

**Partial response** will be defined as a reduction of more than 50% in the diameter of a palpable or visible tumor.

**Stable disease** will be defined as no change in diameter of palpable or visible tumor or a reduction of up to 50% in the diameter of a palpable or visible tumor.

**Disease progression** will be defined as increase of 20% in either perpendicular diameter of a palpable or visible tumor.

### 6.2.3 Measurement of Wound Size

Wound size will be measured post-excision to all subjects.

### 6.2.4 Photographs of Target Tumor

Photographs of the target tumor will aid in tracking the changes in the tumor. Photographs of the target tumor should be taken at the pre-study screening visit before and after biopsy, at the treatment initiation visit, at each interval visit, at the Mohs surgery visit, and at study exit visits.

## 6.3 HISTOPATHOLOGIC EVALUATION

### 6.3.1 Histologic Subtype Definitions

Histologic subtypes will be assigned according to the standard classification into infiltrative/morpheaform, nodular, or subtypes (Sexton et al, 1990.) Tumors with more than one subtype (i.e. “mixed” subtype) will be categorized by the most aggressive subtype. The tumor subtypes will also be recorded by their percentage comprising the BCC tumor.

Histologic subtypes will be defined as Table 1.

Histologic subtype	Definition
Nodular (70%)	Large and small, well-circumscribed nests of basaloid cells in the dermis, accompanied by slit-like retraction from surrounding stroma
Superficial (10-15%)	Proliferation of atypical basaloid cells parallel and superficially confined to the epidermis with slit-like retraction of the palisaded basal cells from subjacent stroma
Morpheaform (5-10%)	One to two cells thick columns of basaloid cells enmeshed in a dense collagenized stroma containing proplastic fibroblasts. The tumors are poorly demarcated, showing widespread invasion of the reticular dermis and penetration in the subcutaneous tissue
Infiltrative (5-10%)	Irregularly sized and shaped nests of tumor cells with sharp angulation of their peripheral contours and occasional foci of slit-like retraction; frequently fibrotic stroma with plumb desmoplastic stromal fibroblasts.

